5. Lack of appetite, nausea, vomiting
6. Dyspnea
7. Headache, pain in the chest, bone pain
8. Priapism
9. Increase/decrease blood pressure
10. Anaphylactic reactions/erythema

Risks for blood draw:

- Occurrence of discomfort and/or a bruise at the site of puncture
- Less commonly, fainting
- The formation of a clot or swelling in the vein and surrounding tissue
- Bleeding from the puncture site
- On rare occasions an infection may develop at the site where the blood is collected

Potential Risks of No Treatment

Since Omegaven® will only be offered to those patients for whom no standard therapy has been safe and effective, the risks of not being treated are those allowing for the natural history of their disease and associated clinical manifestations to progress. These include fulminate liver failure and death.

VII. Overall Risk Assessment

Patients will be at some risk inherent in taking a pharmaceutical agent that has not been fully evaluated for long duration treatment. However, the availability of safety data demonstrates no life-threatening risks or toxicities to vital organs or physiologic functions. The potential benefits of Omegaven® in this patient population are mainly based on human trials and our own experience.

VIII. Risk Category

The research involves greater than minimal risk, but presents the prospect of direct benefit to the individual subjects.

IX. Methods

A. Subject Selection

No concomitant medications will prohibit enrollment.

Inclusion Criteria

1. Males and females ages one month of age to 18 years of age
2. Patients with intestinal failure on TPN
3. Patients who have a conjugated or direct bilirubin of ≥ 3 mg/dl for more than 4 weeks and in whom other causes of cholestasis have been excluded with reasonable certainty utilizing biochemical, serologic, microbiologic, and radiographic techniques. Liver biopsy is not required to rule out other disorders, but may be utilized at the clinician's discretion
4. Patients in whom reduction of IV soy-based lipid load to an **average** <1.2 g/kg body weight/day has failed to reduce the conjugated or direct bilirubin within ≥ 30 days of implementation

5. Willing to use birth control during study participation for females of child-bearing potential, as determined by investigator.
6. Signed informed consent for use of Omegaven® obtained

Exclusion Criteria

1. Any of the contraindications to use of Omegaven®

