The primary endpoint will be reduction in conjugated or direct bilirubin level to below 1 mg/dl. Data from previous retrospective analyses and prospective uncontrolled studies suggest that from the inception of Omegaven® therapy, conjugated or direct bilirubin will remain elevated for approximately 8 weeks at levels comparable to those observed prior to administration of Omegaven®. Subsequently, levels are expected to fall by approximately 1 mg/dl/week until they normalize. The time to normalization will vary according to each patient's baseline conjugated or direct bilirubin level. Thus, a patient who begins Omegaven® with a conjugated or direct bilirubin level of 7 mg/dl is likely to experience normalization within 14 weeks (8+6 weeks). We will compare the group receiving Omegaven® with historical controls from our internal registry who have demonstrated cholestasis while on Intralipid®. We will compare changes in conjugated/direct bilirubin concentration over time between groups via Kaplan-Meier analysis (see Statistics section XIII).

Secondary endpoints will be: normalization of total bilirubin and liver enzymes. Differences in these values at the end of 14 weeks of therapy will be compared with those of controls via Kaplan-Meier analysis identical to that employed for conjugated and direct bilirubin levels. Furthermore, we expect that elevated triglyceride levels which might be present at the initiation of therapy will have normalized at the same time that liver profiles have normalized.

XI. Assessment of Safety/Data Safety Monitoring Board

A DSMB will monitor the study for the occurrence of adverse events (both serious and otherwise). A significant increase in the rate of adverse events would be cause for concern for the safety of participants in the study. Information on adverse events will be presented in several ways: (1) listings of serious adverse events with accompanying narrative summary by the PI; (2) summaries of adverse events by body system and type of event. This information will be presented to the DSMB.

The DSMB will also monitor the efficacy and the conduct of the study. Interim monitoring reports for the DSMB will include, but will not be limited to, such tabulations as:

1. platelet counts
2. essential fatty acid profiles
3. coagulation studies
4. liver profiles

5. renal profiles

The DSMB will meet at least once per year and possibly more frequently given the expected speed of recruitment and study medication administration.

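### The secondary endpoints are compared at 14 weeks, before total bilirubin is expected to normalize in children who enter with direct bilirubin above about 7 mg/dl

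*Combined protocol and SAP*

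**What the plan says.** All the efficacy statements are in Section X.

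- Primary endpoint: "The primary endpoint will be reduction in conjugated or direct bilirubin level to below 1 mg/dl". No time limit is attached.
- Expected course on Omegaven: "conjugated or direct bilirubin will remain elevated for approximately 8 weeks at levels comparable to those observed prior to administration". Then: "Subsequently, levels are expected to fall by approximately 1 mg/dl/week until they normalize". The section adds that time to normalization depends on the child's baseline level.
- Illustration: a child starting at 7 mg/dl "is likely to experience normalization within 14 weeks (8+6 weeks".
- Secondary endpoints: "Secondary endpoints will be: normalization of total bilirubin and liver enzymes".
- Secondary analysis: "Differences in these values at the end of 14 weeks of therapy will be compared with those of controls via Kaplan-Meier analysis". The same sentence describes it as a "Kaplan-Meier analysis identical to that employed for conjugated and direct bilirubin levels".

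Entry (Section IX.A, inclusion criterion 3) is open to "Patients who have a conjugated or direct bilirubin of ≥ 3 mg/dl for more than 4 weeks". No upper limit is set. Under Section IV, treatment continues until TPN is no longer needed, or until bilirubin is normal and enteral lipid suffices. It is not capped at 14 weeks. Section IX.F repeats the baseline blood tests, including the liver profile, twice a month for 6 months and monthly after that while the child is on Omegaven.

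**The concern.** Section X says that time to normalization differs between children according to baseline, then compares the secondary endpoints for all of them at one time. That time equals the predicted time for the single example child, and no other reason for it is given. Because entry has no upper bilirubin limit, some eligible children are expected to normalize only after the comparison is made.

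The sentence also leaves the analysis undefined. A difference in values at a set week is a landmark comparison, whereas Kaplan-Meier estimates time to an event. Calling the method identical to the primary's does not settle which is meant, because the primary has no 14-week limit. Different analysts could produce different results from the same data. On some readings, normalizations that the protocol itself expects after week 14 would not be counted.

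**Working it through.** **Inputs, all from Section X unless noted**

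- Lag before decline: about 8 weeks.
- Rate of fall: about 1 mg/dl per week.
- Threshold for direct bilirubin: 1 mg/dl.
- Time of secondary comparison: 14 weeks.
- Entry level: 3 mg/dl or more, no upper limit (Section IX.A).

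**Formulas, for baseline direct bilirubin B**

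- Weeks to reach 1 mg/dl: t(B) = 8 + (B − 1)/1.
- Direct bilirubin at week 14, for B of 7 or more: B − 1 × (14 − 8) = B − 6.

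**The plan's own figure.** t(7) = 8 + 6 = 14 weeks. This reproduces the example.

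**Other baselines**

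| Baseline direct bilirubin (mg/dl) | Expected direct bilirubin at week 14 (mg/dl) | Expected week of reaching 1 mg/dl |
|---|---|---|
| 3 | already normal | 10 |
| 7 | 1 | 14 |
| 8 | 2 | 15 |
| 10 | 4 | 17 |
| 12 | 6 | 19 |
| 15 | 9 | 22 |

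**Boundary.** The largest baseline expected to reach 1 mg/dl by week 14 is 1 + 1 × (14 − 8) = 7 mg/dl.

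**Softness of the boundary.** The protocol calls both the lag and the rate approximate. With lag L and rate r the boundary is 1 + r × (14 − L). I assumed L from 7 to 9 weeks and r from 0.75 to 1.25 mg/dl per week; these ranges are not in the documents.

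- Slowest case: 1 + 0.75 × (14 − 9) = 4.75 mg/dl.
- Fastest case: 1 + 1.25 × (14 − 7) = 9.75 mg/dl.

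**From direct to total bilirubin.** The course is stated for direct bilirubin only. Total bilirubin cannot be lower than its direct fraction, so at week 14 it is at least B − 6. The documents give no normal limit for total bilirubin. With an assumed limit of 1 mg/dl the boundary stays at 7; with 1.2 mg/dl it is 1.2 + 6 = 7.2.

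**Liver enzymes.** The documents give no lag, rate or threshold, so nothing can be calculated.

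**What the sentence could mean for a child with baseline 10**

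- Levels compared at week 14: the fall in direct bilirubin from 10 to about 4 counts as benefit.
- Proportions normalized by week 14: the child counts as not normalized.
- Kaplan-Meier truncated at week 14: the child is censored there, and the normalization expected at about week 17 or later is lost.
- Kaplan-Meier over all follow-up, as for the primary: that normalization is counted if it is observed.

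**The case against.** The strongest reply is that comparing or truncating Kaplan-Meier curves at a fixed time is ordinary practice, that any finite horizon leaves some children not yet normalized, and that the rule applies to both groups. That is correct as far as it goes. What stands is that the documents do not justify this horizon, that it fits poorly with the course stated just before it, and that the primary analysis it is said to copy has no such limit.

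A reader might infer more than the documents support:

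- **That the protocol predicts failure for every child above 7 mg/dl.** It does not. The figures are approximate, they concern direct bilirubin, and nothing is said about when enzymes normalize. A child not normalized at week 14 may simply be censored. Nor should the example child be faulted for reaching exactly 1.0 rather than below 1; the illustration is rounded.
- **That 14 weeks was copied from the example.** This is likely but not stated.
- **That the comparison is diluted toward no difference, or driven mainly by baseline mix.** Neither can be shown. The baseline distribution is not given, and Section XIII plans adjusted Cox models, although it names no covariates. Section III says about a quarter of infants recover even on soy lipid if the bowel adapts, so a later horizon could also let controls catch up.

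The calculation also rests on one of two expectations that do not agree. Section XIII assumes about 50% resolution within 8 weeks on Omegaven, while the Section X course puts even a baseline of 3 mg/dl at week 10. If Section XIII is nearer the truth, fewer children would be unresolved at week 14. That inconsistency is a separate matter; the undefined secondary analysis remains either way.

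**Conclusion.** The point holds for total bilirubin. On the Section X course, children entering with direct bilirubin above about 7 mg/dl are expected still to have raised total bilirubin at week 14. The excess grows with baseline: at least about 2 mg/dl total at a baseline of 8, and at least about 9 mg/dl at a baseline of 15. This rests on the approximate 8-week lag and 1 mg/dl weekly fall, and on an assumed upper normal limit near 1 mg/dl.

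For liver enzymes the conclusion is narrower: the 14-week time is unexplained, and no prediction can be made. For both endpoints the sentence needs to say which analysis is intended.

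The consequence is loss of expected later events and of sensitivity. Its size is unknown because the share of children above the boundary is not given. The primary endpoint is unaffected. The change should be made, but it concerns secondary endpoints only.

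**What to change.** In Section X, delete the clause that sets the comparison at 14 weeks. Define each secondary endpoint as time to normalization over the same follow-up as the primary endpoint, censoring at the last measurement. Apply the same maximum follow-up to treated children and registry controls. For each endpoint, include only children whose value is abnormal at baseline, so that a normal day-0 value is not counted as a normalization.

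Moving the reading to a later fixed time, such as 26 weeks, would not solve the problem. Setting 8 + (B − 1) = 26 gives B = 19, so the same difficulty returns above about 19 mg/dl. Children who finish treatment early may also have no value at that time, since the final visit is within 1 month of stopping (Section IX.F).

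The cost is one sentence. Treated children need no extra sampling, because the liver profiles are already scheduled. The denominator for enzymes will be somewhat smaller. The sponsor must confirm that registry follow-up of the controls, which the documents do not describe, supports the chosen horizon.

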 - Impaired lipid metabolism (triglycerides >1000 mg/dL) while on 1g/kg/day or less of Intralipid
 - History of severe hemorrhagic disorders (ie. hemophilia, Von Willebrand disease, etc.)
 - Unstable diabetes mellitus
 - Collapse and shock
 - Stroke/Embolism
 - Cardiac infarction within the last 3 months
 - Undefined coma status
 - Pregnancy (positive pregnancy test) prior to enrollment in the study for females of child-bearing potential
 - Females of child-bearing potential who are unwilling to use birth control during study participation
2. Parental decision to forego the use of Omegaven®
3. Known fish or egg allergy
4. Pregnancy
5. Causes of liver disease other than PNAC

B. Withdrawal Criteria

1. Decision of an assenting minor/adult subject or parent/guardian to withdraw from the study*
2. Anaphylaxis
3. Evidence of spur cell anemia.
4. Increasing anemia (hemoglobin < 7 g/dL) in the absence of gastrointestinal bleeding.
5. Mucosal bleeding or bleeding from IV insertion sites requiring transfusion.
6. Reproducible priapism associated temporally with the infusion
7. Mucosal bleeding associated with abnormal platelet function
8. Bowel adaptation such that patient can either come off TPN or such that enteral fat can meet the patient's nutritional requirements
9. Patient undergoes liver transplantation
10. Pregnancy
11. Patient is lost to follow up

* If an assenting minor chooses to withdraw from the study early, even if the parent wants the child to participate, the child will have their wishes respected.

C. Stopping Rules

If two subjects develop the same grade-3 adverse event (including liver function tests, Protocol – Compassionate Use of a Fish Oil-derived Intravenous Fat Emulsion (Omegaven®) to Reverse Parenteral Nutrition (PN) Induced Cholestasis

coagulation profile, and platelet count) related to the study medication that is irreversible upon de-escalation (does not reverse after 10 days) or upon discontinuation of the study drug, or any subject develops a related grade-4 adverse event, these events will be the cause for termination of the study.

D. Monitoring for toxicity due to Omegaven®

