Potential toxicity will be assessed by analyzing clinical and laboratory parameters including serum electrolytes, hematological studies, serum triglycerides, total cholesterol, liver function tests, and essential fatty acid profiles where applicable. Blood samples will be taken in accordance with current institutional standards for monitoring hyperalimentation. In the face of mucosal bleeding, studies of platelet function (closure time) will also be performed.

E. Patient Recruitment and Consenting Process

Patient Recruitment

Approximately 25 patients, ages one month to 18 years will be enrolled from Cincinnati Children's Hospital. All patients will be enrolled as inpatients. The study will be explained in detail by the physician and study coordinator and the consent form (and age appropriate assent forms) will be reviewed per institutional IRB requirements. These subjects will be recruited through the Division of Gastroenterology, Hepatology, and Nutrition, the Department of Surgery, or the Division of Neonatology. The prospective patients will be identified through the clinical staff within all three divisions working collaboratively. The clinical staff will initially inform potential subjects and families about the research study. The research staff will notify and obtain permission from the patient's primary gastroenterologist, surgeon, or neonatologist before contacting the family.

Subjects who drop out prior to drug initiation may be replaced with new subjects until target enrollment is achieved, as these will not have been given study medication.

Consenting Process

For those patients meeting inclusion criteria, the study purpose, procedures, costs, risks, benefits, and alternatives to participation will be thoroughly explained and presented to the patient and their family by the designated study coordinator and/or investigator, and subjects will be screened for willingness to participate. Subjects and parents will be explicitly informed that choosing not to participate will in no way affect the quality of the medical care that they will receive. Once patients and families have had enough time to consider participation and have expressed a willingness to participate, informed consent will be obtained from the parents or legal guardian and child assent when appropriate based on age and institutional IRB requirements.

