6. is an event that does not meet the above criteria but may jeopardize the patient or may require medical or surgical intervention to prevent one of the outcomes listed above.

IRB Notification of SAEs

Per CCHMC Institutional Review Board (IRB) Requirements, the Investigator will report adverse events to the IRB Office within the appropriate timelines documented in the institutional policies for reporting SAE and AE . .

SAE's require expedited reporting when meeting the following criteria:

- The incident is serious
- Unexpected – any adverse experience, the specificity or severity of which is not consistent with the underlying disease of the patient or with the risk described in the protocol
- At least possibly related to the study agent or other protocol specific activity

Recording of Adverse Events

Adverse event recording will begin after administration of study medication.

Diagnostic and therapeutic non-invasive and invasive (i.e. surgical) procedures will not be reported as adverse events. However, the medical condition for which the procedure was performed must be reported if it meets the definition of an adverse event, unless it is pre-existing (prior to initiating Omegaven®).

Medical conditions/diseases present before starting drug are only considered adverse events if they worsen after starting treatment.

Symptoms of the original or targeted disease are not to be considered adverse events in this treatment. The following symptoms are indicative of underlying disease and will not be reported as adverse events:
hyperbilirubinemia, elevated creatinine/renal failure, weight gain, encephalopathy, hypoxia / respiratory failure, ascites, hepatomegaly and right upper quadrant pain, sepsis (culture positive or negative), emesis or

increase in stool output with the advancement of feeds or bleeding due to liver failure.

Abnormal laboratory values or test results constitute adverse events if they induce clinical signs or symptoms or require therapy. They are to be recorded on the Adverse Events CRF under the signs, symptoms or diagnoses associated with them.

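### The list of disease symptoms exempt from adverse-event reporting does not separate out events that are new on treatment and possibly drug-related, so these may go ungraded and uncounted under the stopping rule

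*Combined protocol and SAP*

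**What the plan says.** Section XII, Recording of Adverse Events, first says that symptoms of the target disease are not adverse events. It then gives a list under the sentence "The following symptoms are indicative of underlying disease and will not be reported as adverse events". The sentence just before this paragraph makes a pre-existing condition an adverse event if it worsens on treatment. The paragraph just after makes an abnormal laboratory result an adverse event if it causes signs or symptoms or needs therapy. Neither refers to the list, and the list refers to neither.

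The stopping rule in IX.C is written in terms of adverse events. One limb reads "If two subjects develop the same grade-3 adverse event (including liver function tests", continuing "coagulation profile, and platelet count) related to the study medication that is irreversible upon de-escalation". The other reads "or any subject develops a related grade-4 adverse event, these events will be the cause for termination of the study".

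Under IRB Notification of SAEs, expedited reporting applies to a serious event that is unexpected, meaning one "the specificity or severity of which is not consistent with the underlying disease of the patient" or with the risks in the protocol, and that is "At least possibly related to the study agent or other protocol specific activity".

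Bleeding has separate provisions. One withdrawal criterion in IX.B is "Mucosal bleeding associated with abnormal platelet function", another is bleeding that requires transfusion, and IX.D adds "In the face of mucosal bleeding, studies of platelet function (closure time) will also be performed".

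**The concern.** Most of the listed items are what advanced cholestasis and intestinal failure produce, and exempting them at their baseline level is sensible. The difficulty is that the exemption is defined by the name of the event. It does not ask whether the event is new, how severe it is, or whether the drug may have caused it.

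A drug cause is not far-fetched for every category. Section VI lists dyspnea, cyanosis, chills, a rise in temperature and blood-pressure changes among possible infusion effects, while respiratory failure and culture-negative sepsis are on the exempt list. Staff would have to decide the cause before recording anything, and that decision might never be documented or reviewed.

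At stake are the protocol actions that need a graded or attributed event, and the adverse-event summaries that serve the secondary aim of confirming safety (Section II).

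**Working it through.** No formula applies. The check is a count of the list and a comparison of the clauses that depend on it.

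**1. The list.** Counting compound entries once:
- No causal qualifier: (1) raised bilirubin; (2) raised creatinine or renal failure; (3) weight gain; (4) encephalopathy; (5) hypoxia or respiratory failure; (6) ascites; (7) hepatomegaly with right upper quadrant pain; (8) sepsis, with or without a positive culture.
- Exempt only for a stated cause: (9) emesis or higher stool output as feeds are advanced; (10) bleeding caused by liver failure.

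That is 10 in all, of which 10 − 2 = 8 are unqualified.

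**2. What depends on being an adverse event.**
- Severity grade and relatedness are assigned to adverse events (XII, Grading; Relationship to Drug).
- The IX.C stopping rule counts adverse events.
- Discontinuation for an attributable Grade > 3 reaction uses that grade and attribution (XII, Relationship to Drug).
- Attributable non-serious events are followed after participation ends (XII, Follow-Up after Adverse Events).

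The last three are actions. Each fails for an event that was never entered as an adverse event.

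**3. Does the serious-event route catch them?** Section XII defines a serious adverse event as an adverse event that meets one of six criteria. The lead-in to the list says that symptoms of the target disease are not to be considered adverse events. Taken literally, a listed event fails at the first step, before seriousness is asked. The DSMB chair's 7-day review in Section XI, which confirms grading and checks the stopping criteria, is attached to SAE reports and inherits the same uncertainty.

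**4. Does other text catch them?**
- *Worsening clause:* covers conditions present before treatment. It is silent on encephalopathy, renal failure or sepsis that begins on treatment.
- *Laboratory clause:* could bring back bilirubin or creatinine that is symptomatic or treated. It does not address clinical events.
- *IX.C wording:* names liver tests, coagulation and platelets. Only liver tests, through bilirubin, overlap the list (1 of 3 groups).
- *Withdrawal criteria in IX.B:* 2 of 11 (numbers 5 and 7) bear on a listed category, and both concern bleeding. That leaves 10 − 1 = 9 categories with no criterion of their own.
- *Data capture:* IX.G collects jaundice, hepatosplenomegaly and ascites. Section XI sends liver and renal profiles, laboratory evaluations and vital signs to the DSMB. This gives visibility, but no grade or relatedness is required.

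**5. Scale.** With about 25 patients, the grade-4 limb needs 1/25 = 4% and the grade-3 limb needs 2/25 = 8% (same event, related, irreversible). These are the thresholds of the rule. They do not measure how many events the list would remove.

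**The case against.** The strongest reply is that a sensible investigator would not read the list this way. Its lead-in speaks of symptoms of the target disease, so an event thought to be caused by the drug is arguably outside it. No text says that a listed event cannot be an SAE. Grade 4 means life-threatening, which is itself an SAE criterion, so if SAE reporting applies, the grade-4 limb is covered by the chair's review. The population is very ill and there is no concurrent control group. Because one related grade-4 event ends compassionate access, limiting attribution of expected disease events may be deliberate.

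Part of this stands. Exempting expected, stable manifestations is right, and the lead-in does support a narrower reading. But eight entries are named outright as indicative of the underlying disease, and the SAE argument assumes the point in question, namely that a listed event is still an adverse event.

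Four stronger readings are tempting and are not supported:
- *That bilirubin is the clearest contradiction.* It is the weaker case. Entry requires conjugated or direct bilirubin of at least 3 mg/dl for more than 4 weeks, so the elevation is not new. The worsening clause, the laboratory clause, the naming of liver tests in IX.C and the DSMB's liver profiles all bear on it. Creatinine is similarly helped by the laboratory clause and the renal profiles. What is missing is a sentence on precedence.
- *That the drug's main named risk, bleeding, is exempt.* Only bleeding due to liver failure is listed. Platelets and coagulation are not, and IX.B and IX.D address mucosal bleeding directly.
- *That the DSMB would not see the data.* It receives laboratory data and vital signs, and its list of tabulations is expressly not exhaustive.
- *That the two descriptions of an unexpected event in Section XII keep listed events out of expedited reporting.* The expedited criteria carry their own severity test, which the later, broader description need not displace. Aligning them is tidying.

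**Conclusion.** The point holds for listed clinical events that are new on treatment and possibly drug-related: renal failure, encephalopathy, respiratory failure and sepsis are the main examples. On the literal text these need not be graded, attributed, counted under IX.C, acted on under the Grade > 3 rule or followed as attributable, and no sentence guarantees that the SAE route applies. For bilirubin and creatinine the problem is limited to unstated precedence among clauses that partly cover them.

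The conclusion assumes that staff follow the list as written. A reader might infer that safety events will be missed in some number, or that the stopping rule is disabled. The documents support neither, because they give no event rates and investigators may resolve the ambiguity sensibly. What can be said is that the rule turns on one or two records among about 25 patients, so whether a single event is recorded can matter. This is a cheap improvement worth making.

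**What to change.** Amend Recording of Adverse Events in Section XII as follows:
- Limit the exemption to listed events that are no worse than the patient's baseline and judged not possibly related to the drug.
- Record any listed event that is new, worse than baseline, serious or possibly related, with date, grade and relatedness.
- Flag such events as disease-related where appropriate, and tabulate them separately for the DSMB.
- State that they count under the unchanged IX.C rule only if judged related, and that serious ones go through the existing 7-day review by the DSMB chair.

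Using one definition of unexpected throughout Section XII is optional.

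The cost is protocol wording plus a few more entries and relatedness judgements for about 25 patients, with no added visits, tests or stopping criteria. The downside is a small chance that disease progression is judged related and counts toward ending a compassionate-use study. The baseline and relatedness conditions reduce that chance without removing it.
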